NCT Number: NCT04627727
Official Title: Effect of a Low FODMAP Diet on SIBO Breath Test Positivity
Document Type: Study Protocol and SAP
Document Date: 05/31/2024

PART B STUDY DESCRIPTION

Title of Protocol	Effect of a low FODMAP diet on SIBO
Principal Investigator	[name], MPH

B1. PURPOSE OF PROTOCOL

The primary objectives of this study are to evaluate the following in patients with SIBO:

1. The effect of LFD on bloating
2. The effect of LFD on hydrogen and methane levels in patients with bloating

B2. SIGNIFICANCE AND BACKGROUND FOR THE STUDY

Bloating is the most common symptom associated with disorders of brain-gut interaction (i.e., functional bowel disorders) such as irritable bowel syndrome, a disorder characterized by abdominal pain and altered bowel habits which affects up to 11% of world population. A common cause of bloating is small intestinal bacterial overgrowth (SIBO), a condition defined by excessive and/or abnormal type of bacteria in the small bowel. The potential role of SIBO for irritable bowel syndrome (IBS) was initially proposed by Pimentel et al. Using lactulose breath tests (LBTs), 78% of patients with IBS were also diagnosed with SIBO. After antibiotic therapy, 48% of patients no longer met the Rome criteria for IBS. A recent systematic review and meta-analysis concluded that the prevalence of SIBO is increased in IBS.

Dietary factors are known triggers of IBS related symptoms up to 65% of IBS patients report symptoms attributed to food. In double-blind, randomized, placebo-controlled trials; fructose and fructans have been shown to induce IBS symptoms in a dose-dependent manner.⁵ In fact, a diet low in fermentable, oligosaccharides, disaccharides, monosaccharides, and polyols (FODMAPs) is the most extensively investigated dietary intervention in IBS. A recent meta-analysis of seven randomized controlled trials comparing a low FODMAP diet (LFD) with various control interventions in 397 participants suggested a 31% greater likelihood in improvement of global IBS symptoms. In patients with diarrhea predominant IBS (IBS-D), Eswaran et al showed that those randomized to LFD had greater reductions in daily scores of abdominal pain, bloating, stool frequency, stool consistency, and urgency than the modified National Institute for Health and Care Excellence (NICE) diet. Others have also shown objective improvement in stool consistency of IBS-D patients with LFD using King's stool chart.

Despite the clinical efficacy of LFD in improving symptoms of IBS-D, its mechanism of action is not clear. Recently, Zhou et al have shown FODMAPs induce colonic tight junction dysfunction and visceral hypersensitivity in rat models, both of which are reversible when rats were fed an LFD. They further showed that this effect of FODMAPs is mediated by microbial dysbiosis and elevated fecal lipopolysaccharide level. However, studies evaluating the effect of LFD on colonic permeability of humans are lacking. Studies have shown significant differences in intra-individual luminal and mucosal microbiome of patients with functional gastrointestinal disorders as well as an increase in *Prevotella* abundance in IBS patients with SIBO as compared with IBS patients without SIBO. Thus, the exact effect of FODMAP on intestinal permeability and mucosal microbiome in humans is not clear and needs further evaluation.

Several studies have also shown increase in the number of mast cells in the colonic mucosa of IBS patients. Although diet is perceived as an important trigger for mucosal mast cell increase and activation reported in IBS-D, it has been poorly investigated. The above reported study by Zhou et al also reported increase in colonic mast cell in rats fed on high FODMAP diet.

B3. DESCRIPTION OF RESEARCH PROTOCOL

A. Study Design – Overview, Methods, Procedures

Study Design

Consenting patients fulfilling the inclusion and exclusion criteria will undergo a 7-day screening period to assess baseline symptoms and then go on a 3-week low FODMAP diet. The total study duration will be approximately 5 weeks with visits at screening and Day 21.

Screening Visit

- Informed consent will be obtained from the subjects.
- Medical history including IBS and SIBO history will be obtained from the subjects
- Blood samples will be obtained
- Glucose SIBO breath test
- Daily questionnaires. Subjects will be instructed on the online daily questionnaires (described below) to be completed for the duration of the study.
- Subjects will be given two stool collection kits for at-home collection. One stool sample will be collected prior to beginning the treatment period. One stool sample will be collected on Day 21.

Visit 2 (Start of Diet/Day 0)

- Subjects will start the low FODMAP diet. Subjects will be told to ingest only Epicured provided items (excluding water) and to avoid eating anything outside of Epicured provided items.
- Baseline stool sample will be returned

Final Visit (Day 21)

- Blood samples will be obtained
- Post-treatment stool sample will be returned
- Glucose SIBO breath test

Low FODMAP diet

Subjects who consent to participate in the study will have low FODMAP meals delivered to their home by Epicured. Epicured is a meal delivery service that provides ready-to-eat low FODMAP meals. Subjects will be required to provide their home address, name, phone number, and email address to Epicured. Epicured will provide meals and snacks to subjects for the duration of the 3-week low FODMAP period. Subjects will be told to only ingest Epicured provided items (excluding water).

Serological tests for intestinal permeability

The following serological markers for intestinal permeability will be assessed: serum lipopolysaccharide (LPS) activity measured with the Limulus Amebocyte Lysate assay (LAL, Hycult Biotechnology, the Netherlands) and serum zonulin levels (Catalog number 30-ZONSHU-E01; ALPCO, Salem, NH). This will be performed in our GI lab at BIDMC.

Serological tests for mast cell activation

Mast cell activation will be measured by tryptase level with the American Research Products assay (ARP, Waltham, MA)

Stool tests

Stool will be collected for 16S rRNA microbiome sequencing.

Concomitant Medications

Subjects will be allowed and advised to continue with their current IBS treatments (excluding rifaximin) as long as it was at a stable dose for 30 days prior to randomization.

Clinical variables

Data will be collected and stored via Research Electronic Data Capture (REDCap). Patients will be automatically emailed a link daily (via REDCap) with a REDCap link to the questionnaires listed below. Patients do not need access to WiFi, but do need Internet access (can be wired). If subjects do not have access to the Internet, they will not be eligible for participation.

- Rome IV Functional Bloating
Patients will be asked to complete a modified version of the Rome IV bloating questionnaire specific to the past 24 hours.
- IBS-SSS
Patients will be asked to record IBS-SSS and most common stool consistency of the day (measured using Bristol stool form scale).
- Diet compliance: Patients will also be asked to record their day's food and drink intake and record whether they were compliant with the FODMAP diet.

In addition, the following questionnaires will be administered at the end of the baseline period as well as the end of the 3-week LFD.

- Patient Reported Outcomes Measurement Information System (PROMIS)
The Patient Reported Outcomes Measurement Information System (PROMIS) is a National Institutes of Health (NIH) set of tools used to provide information on patient outcomes in a variety of fields.
- Gastrointestinal PROMIS scales: PROMIS scales of belly pain, constipation and diarrhea will be administered to assess the severity of belly pain and diarrhea in our patients. PROMIS Belly pain questionnaire and PROMIS diarrhea questionnaire have five and six questions, respectively, which assess symptom severity on a 5 point Likert scale. Higher T-scores on these questionnaires refer to more severe gastrointestinal symptoms.
 - PROMIS belly pain asks how often did you have belly pain, severity of belly pain, interference with activities, bothersomeness and discomfort.
 - PROMIS diarrhea asks how many days did you have loose stools, interference with activities, bothersomeness, and how often you experience urgency.
 - PROMIS constipation asks how often did you experience hard stools, straining and incomplete evacuation.

Blood Collection

Any blood that is remaining after the analysis is completed will be stored frozen indefinitely at BIMDC for use in future studies. The sample will remain de-identified, but be labeled with the unique subject code. Information related to the subject's diagnosis, treatment, and study results will be retained and possibly used in future analysis and more information becomes identified regarding functional bowel disorders. PHI related to the stored samples will not be used in the future analysis and will be kept on BIDMC's secure server. Any samples that may be shared with collaborators will contain the subject code, but will not have any identifiable information or PHI.

B. Statistical Considerations

Sample Size Justification:

This study aims to recruit 30 subjects until 20 subjects are enrolled.

Data Analysis:

All continuous variables will be tested for normality using the Shapiro-Wilk test. Normally distributed continuous data will be presented as mean (\pm SD) and will be compared pre-and post-dietary interventions using paired Student's t-test. Continuous data which are not normally distributed will be presented as median (range) and compared using Wilcoxon signed-rank test. Proportions will be expressed as percentages and compared using chi-square test or fisher exact test as appropriate. Since we anticipate that most of our tests will involve continuous data that is normally distributed, we based our power analysis on pre-post comparisons using paired t-tests. Assuming two-tailed tests, with alpha set at 5%, a sample size of 20 will provide 80% power to detect a medium effect size (i.e., Cohen's $d=.5$) when the pre-post correlation is $r=.7$.

C. Subject Selection

Patients with functional bloating diagnosed per Rome IV questionnaire and without any alarm features (rectal bleeding, weight loss, nocturnal symptoms, family history of inflammatory bowel disease or celiac disease) will be considered for the study if they had:

- i) Aged 18-65 years at the time of screening

Exclusion criteria

- i) individuals already on a LFD or other dietary restriction such as gluten free diet within the past 6 months
- ii) individuals with peanut, soy, or seafood allergies or insulin-dependent diabetes
- iii) known history of celiac disease, inflammatory bowel disease or microscopic colitis
- iv) prior small bowel or colonic surgery or cholecystectomy
- v) pregnant patients
- vi) antibiotics, excluding topical, in the past 3 months

B4. POSSIBLE BENEFITS

Subjects may experience improvement in their bloating symptoms.

B5. POSSIBLE RISKS AND ANALYSIS OF RISK/BENEFIT RATIO

Blood Drawing

The risks and discomforts of blood drawing from a vein include the possibility of pain or bruising at the site of the blood draw; occasional feeling of lightheadedness; and rarely, infection at the site of the blood draw.

There is a possible risk of loss of confidentiality, however every effort will be made to ensure patient confidentiality which includes but is not limited to only discussing medical information in a private clinical setting and collecting information necessary to accomplish the research purpose. Physical data will be kept in a locked room that only the research team have access to. Electronic data will be kept on the secure server with access granted only to the individuals on the research staff.

B6. RECRUITMENT AND CONSENT PROCEDURES

Recruitment

Patients will be identified in the following ways:

- Clinical practice of the Center for Functional Bowel Disorders and GI Motility at BIDMC
- GI referrals from BIDMC
- Review of medical records, data repositories, and appointment logs
- Clinical Query 2
- Advertisements

Recruitment letters or postcards with opt-in information will be mailed to potential study participants identified through Clinical Query 2, GI referrals, and review of medical records, databases, and appointment logs. A study coordinator will also be present in the motility lab where the breath tests are conducted to recruit any potential study participants.

Participants who are recruited through the means listed above will then be contacted by phone and a brief phone screening will be initiated to assess the subject's eligibility before scheduling the office visit.

Consent

During the screening visit the Investigator will fully explain the purpose of the study to the patient and all questions and concerns regarding the study will be addressed as well (informed consent process) in a private area in the Division of Gastroenterology.

B7. STUDY LOCATION

Privacy

Every effort will be made to ensure the patient's privacy which includes but is not limited to only discussing medical information in a private clinical setting and collecting information necessary to accomplish the research purpose.

Physical Setting

Study visits will be conducted in the Division of Gastroenterology

B8. DATA SECURITY

Physical data will be kept in a locked room that only the research team has access to. Electronic data will be kept on BIDMC server.

B9 Multi-Site Studies

Is the BIDMC the coordinating site? Yes No

Is the BIDMC PI the lead investigator of the multi-site study? Yes No

B10 Dissemination of Research Results

Subjects will be thanked for their participation following their participation in the study and informed of the possibility of future publications.

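### The primary objectives claim an effect of the diet, but a single unblinded group with pre/post tests can only show change during the diet

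*Combined protocol and SAP*

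**What the plan says.** The two primary objectives in B1 are "The effect of LFD on bloating" and "The effect of LFD on hydrogen and methane levels in patients with bloating".

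Under Study Design in B3.A, eligible patients "will undergo a 7-day screening period to assess baseline symptoms and then go on a 3-week low FODMAP diet". The Low FODMAP diet paragraph applies to everyone: "Subjects who consent to participate in the study will have low FODMAP meals delivered to their home by Epicured". Patients know what they receive: at Visit 2, "Subjects will start the low FODMAP diet", with the instruction to eat only the provided items. No control diet, sham diet, waiting list, crossover, blinding or external comparator is described. The word randomization occurs once, under Concomitant Medications, where existing treatment may continue "as long as it was at a stable dose for 30 days prior to randomization". No allocation procedure or second group stands behind it.

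Under Data Analysis in B3.B, normally distributed continuous data "will be compared pre-and post-dietary interventions using paired" t-tests, with the Wilcoxon signed-rank test as the non-normal alternative. The power statement is also for a pre/post comparison: two-sided 5%, n = 20, d = 0.5, r = 0.7, 80% power. No section says what a significant pre/post change may be taken to mean, and the study is not labelled pilot or exploratory.

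**The concern.** A paired test asks whether the mean change is zero. The objectives ask whether the diet caused the change. The two questions coincide only if nothing else moves the outcome over about four weeks, and the plan neither argues this nor states it as an assumption.

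The alternatives differ by objective. Bloating is reported by patients who know they are being treated and who receive delivered meals, so placebo response is the main rival explanation, followed by drift. Hydrogen and methane are instrument readings, so expectation matters less. They rest on one glucose breath test before and one after the diet, which leaves test-retest variation and drift.

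What is at stake is the conclusion. The 5% error rate protects against declaring a change when there is none. It gives no such protection against declaring a diet effect when there is none.

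**Working it through.** **Inputs from B3.B:** n = 20 pairs, two-sided alpha 5%, d = 0.5, r = 0.7. **Assumed, because the document gives no figure:** non-diet shifts of 0.2, 0.3 and 0.4 SD.

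**Step 1: reproduce the plan's power.** With equal SDs before and after, the standardised paired effect is dz = d / √(2(1 − r)) = 0.5 / √0.6 = 0.645. The noncentrality is 0.645 × √20 = 2.89 on 19 df, with critical value 2.093. Power is 78.2%, against the stated 80%; 21 pairs would give 80.3%. The plan's figure is reproduced closely enough.

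**Step 2: what that power refers to.** The formula contains only the size of the mean change, not its cause. A 0.5 SD improvement with no diet contribution is also declared significant 78% of the time.

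**Step 3: smaller non-diet shifts, true diet effect zero.** The same formula with the shift s in place of d:

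| Shift s (SD) | dz = s/√0.6 | Noncentrality dz × √20 | Trials with p < 0.05 |
|---|---|---|---|
| 0 | 0 | 0 | 5% |
| 0.2 | 0.258 | 1.15 | 20% |
| 0.3 | 0.387 | 1.73 | 38% |
| 0.4 | 0.516 | 2.31 | 59% |

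For the non-zero shifts, almost all of these rejections are in the direction of the shift.

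**Step 4: regression to the mean, bloating.** This needs the value that selected the patient to serve also as the baseline. B3.C selects on a diagnosis: "Patients with functional bloating diagnosed per Rome IV questionnaire". B3.A takes baseline symptoms from a separate 7-day period with daily questionnaires about the past 24 hours. A simulation took patients from the upper half of a population on the selecting measure, with separate baseline and post values and all three pairwise correlations equal (an assumption). The mean change was about zero, and significant improvement occurred in about 2.5% of trials, the nominal one-sided rate.

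**Step 5: regression to the mean, breath gases.** B1 describes patients with SIBO, and a glucose breath test is done at screening, but the criteria in B3.C require no positive test. Only if that screening test is also used to establish SIBO would one reading both select the patient and serve as baseline. The document does not say so, and no size is attached here.

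**The case against.** The strongest reply is that a 20-patient single-arm study is a legitimate choice, that readers know its limits, and that the background in B2 already cites randomized comparisons of the diet with control interventions. The design is indeed not the defect, and no control arm is being asked for. But evidence from other trials does not make this trial's contrast causal, and the protocol never states the limit. The mismatch between objective and test stands.

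Three stronger readings are tempting and are not supported.

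- A reader might infer that regression to the mean alone would produce much of the targeted bloating change. If the selecting value were also the baseline, with patients from the upper half of a population with r = 0.7, the expected null fall would be 0.24 SD, significant in about 28% of trials. The plan separates the two measurements, so this is not the design described. It also misapplies r: the plan's 0.7 concerns the enrolled sample, and matching it after such selection needs a population correlation of about 0.85, giving about 0.12 SD and 16% of trials. No severity threshold for entry is given, so the degree of selection has no anchor. What remains is that the plan does not say how the seven days are summarised.
- A reader might infer that the sponsor will report any change as a diet effect. The document contains no results language. The point rests on the wording of the objectives and the absence of a caveat.
- A reader might expect a model of the daily diaries, with a slope and a step at Day 0, to isolate the diet effect. Placebo response also begins at Day 0, so the step would absorb it. If a true benefit built up linearly to 1.0 by the last diet day and one common slope were fitted, the step would be about −0.12, the wrong sign. The diaries also say nothing about breath gases, which are measured only twice.

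**Conclusion.** The point holds as a mismatch between causal objectives and a design that estimates within-patient change. It applies to both primary objectives: placebo response bears mainly on bloating, test-retest variation and drift on both. With no diet effect, the planned test would be significant in about 20%, 38% or 59% of trials under non-diet shifts of 0.2, 0.3 or 0.4 SD. Those rates rest on the plan's n and r, equal SDs before and after, and approximate normality. The shift sizes are illustrative, and the documents give no basis for choosing among them. Regression to the mean is secondary for bloating and conditional for breath gases. The matter is worth correcting because it changes what the trial may conclude, but it is corrected by wording.

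**What to change.** 1. In B1, replace the two effect statements with: change from baseline in bloating, and in hydrogen and methane, during a 3-week delivered low FODMAP diet.
2. In B3.B, add that a significant paired test will be reported as within-patient change and will not be attributed to the diet.
3. Reconcile the reference to randomization under Concomitant Medications with the one-group design described elsewhere in B3.

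No extra patients, data or analyses are needed. The cost is an amendment to the text and a weaker headline claim. If the sponsor wishes to keep a causal objective, a concurrent control and a new sample size would be needed. At d = 0.5, r = 0.7 and 80% power, the normal approximation gives 2 × (1.96 + 0.84)² × 0.6 / 0.25, or 38 per arm, on change scores. With baseline adjustment, 1 − r² = 0.51 replaces 0.6, which gives 33 per arm. That is 66 to 76 patients in all, a different trial from the one planned.

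### Daily Bristol stool form has no analysis of its own, and the plan's default signed pre/post test would not measure improvement in a group with mixed bowel habits

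*Combined protocol and SAP*

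**What the plan says.** Under Clinical variables in B3.A, in the IBS-SSS item, patients record daily the "most common stool consistency of the day (measured using Bristol stool form scale". The same section adds symptom scales at the end of baseline and the end of the diet: "PROMIS scales of belly pain, constipation and diarrhea will be administered".

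Entry under B3.C is for "Patients with functional bloating diagnosed per Rome IV questionnaire and without any alarm features". Neither the inclusion nor the exclusion list contains a bowel-habit or IBS-subtype criterion.

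The Data Analysis text in B3.B gives general rules by type of variable. Normally distributed continuous data "will be compared pre-and post-dietary interventions using paired Student's t-test". For the rest, "Continuous data which are not normally distributed will be presented as median (range) and compared using Wilcoxon signed-rank test". A third rule reads: "Proportions will be expressed as percentages and compared using chi-square test or fisher exact test as appropriate". The text does not name the Bristol scale, say whether it is continuous, ordinal or categorical, reduce the daily values to one value per patient, define a normal range, or stratify by baseline bowel habit.

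The primary objectives in B1 are bloating and breath hydrogen and methane. Stool form is not among them.

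**The concern.** On most scores in this trial, a fall or a rise means the same thing for every patient. On the Bristol scale it does not: a lower value is improvement for a patient with loose stools and worsening for a patient with hard stools. A signed mean or median change therefore measures movement toward firmer or looser stool, not improvement.

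The background in B2 cites better stool consistency on the diet in diarrhea-predominant IBS, where one direction is the good one. This trial enrols functional bloating without regard to bowel habit, so that reading does not carry over. If the raw score goes through the default rule in a mixed group, a diet that brings stool form toward normal can look weak or null. A significant result could not be read as benefit without knowing who moved and from where. Choosing Wilcoxon over the t-test does not help, since both work on signed differences.

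**Working it through.** **Inputs from B3.B:** n = 20, two-tailed alpha 5%, Cohen's d = 0.5, pre-post correlation r = 0.7, stated power 80%.

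**Inputs assumed:** the scale has its normal value in the middle (a general property of the instrument, not stated in the documents); every patient starts on one side of normal and moves toward it; the share on each side is varied because the documents give none.

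**Step 1. Reproduce the plan's figure.** The standardised paired effect is dz = d / sqrt(2(1 - r)) = 0.5 / sqrt(0.6) = 0.6455. The noncentral t with 19 df gives power 78.2%; the normal approximation gives 82.3%. The stated 80% is reproduced to within about 2 points. It is a generic figure, not one for stool form, and nothing here overturns it.

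**Step 2. Apply the same effect to a two-directional score.** Each patient moves 0.6455 SD of change toward the middle. If a share p starts on the minority side, the signed mean change is 0.6455 × (1 - 2p). At p = 0.20 it is 0.6455 × 0.60 = 0.387; at p = 0.50 it is 0. The two directions also pull patients' changes apart, which inflates the SD in the denominator of the test. Power of the paired t-test, from 100,000 simulated trials per mix with n = 20 and the mix held fixed:

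| Mix (patients) | Signed mean change, SD units | Power, signed score | Power, change scored toward the middle |
|---|---|---|---|
| 20 / 0 | 0.645 | 78% | 78% |
| 18 / 2 | 0.516 | 53% | 78% |
| 16 / 4 | 0.387 | 28% | 78% |
| 15 / 5 | 0.323 | 19% | 78% |
| 14 / 6 | 0.258 | 12% | 78% |
| 12 / 8 | 0.129 | 4% | 78% |
| 10 / 10 | 0 | 2% | 78% |

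Power falls below 5% near balance because the mix is fixed: the spread between the two directions enlarges the estimated SD but adds nothing to the variability of the mean.

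**Step 3. Vary the effect.** With a larger assumed effect (each patient moves 1 point, SD of change 1) and the mix drawn at random, the signed change has mean 1 - 2p and SD sqrt(1 + 4p(1 - p)). At p = 0.25 that is 0.5 / sqrt(1.75) = 0.378, and power is 36%, against 99% at p = 0. At p = 0.40 it is 0.2 / sqrt(1.96) = 0.143, and power is 9%. A stronger diet effect does not remove the problem.

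The last column of the table is a best case. It assumes that nobody starts in the normal range and nobody crosses the middle. Patients with normal baseline stools have no room to improve and would weaken any summary of improvement.

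**The case against.** The strongest reply is that B3.B prescribes nothing wrong for stool form, because it prescribes nothing for it at all. A reader might infer that the plan analyses the Bristol score as an ordinary continuous variable. That is an inference from the default, and the documents do not state it. This stands, and the point is worded accordingly. The proportions rule is not a clear way out, however: no category is defined, and chi-square and Fisher tests compare independent groups, whereas these are the same patients before and after.

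A reader might also infer that opposite improvements simply cancel. Full cancellation needs a near-balanced mix, and the documents give none. Offering both a constipation and a diarrhea scale does not establish one; the stated purpose of those scales mentions belly pain and diarrhea only.

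Nor do the documents support saying that the plan would count firmer stools in a constipated patient as benefit. They define no direction of benefit for stool form, and the tests are two-tailed.

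Finally, the stakes are limited. Stool form is in no primary objective and was not singled out in the power calculation. The PROMIS diarrhea and constipation scales measure each direction separately, before and after the diet. This stands as mitigation. But those scales are given at two time points only, and they do not make the daily stool record interpretable.

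**Conclusion.** The point holds as a gap with an unsuitable default. Stool form is collected daily, no analysis is named for it, and the only pre/post rule for scores is a signed test that does not measure improvement on this scale when bowel habits are mixed. Under the plan's own effect size, 4 of 20 patients on the minority side would lower power from 78% to about 28%, so a balanced mix is not needed for a serious loss.

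These figures rest on an assumed mix, on every patient being abnormal at baseline and moving toward normal, and on the scale having its normal value in the middle. If nearly all enrolled patients share one bowel habit, the loss is small. The outcome is supportive and no conclusion on the primary objectives is affected, so this is a low-cost improvement worth making. A reader might also suspect that the daily form has no way to record a day without a stool; the form is not shown, so the documents do not support that claim.

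**What to change.** In B3.B, state that stool form is summarised per patient as the percentage of recorded stool days in a pre-defined normal range, or as mean distance from the middle of the scale, in the baseline week and in the last week of the diet. Compare the two periods with a paired t-test or Wilcoxon signed-rank test. Name one of the two summaries as the one to be tested, and have the investigators fix the range before any stool data are examined. Report the raw signed change only separately for patients with predominantly hard and predominantly loose stools at baseline, with the number in each group.

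The cost is a few lines of wording and a little more analysis work. The data are already being collected, so no patients, visits or samples are added. The downside is that the result depends on the chosen normal range, which is why it must be set in advance.

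### Does letting a Shapiro-Wilk check on each variable choose the paired test, without mentioning within-patient differences, undermine the pre-post comparisons?

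*Combined protocol and SAP*

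**What the plan says.** The whole analysis rule is in section B3.B (Statistical Considerations, Data Analysis) of the combined protocol and SAP. It opens with "All continuous variables will be tested for normality using the Shapiro-Wilk test". Variables judged normal are summarised by mean and SD and "will be compared pre-and post-dietary interventions using paired Student's t-test". For the rest, "Continuous data which are not normally distributed will be presented as median (range) and compared using Wilcoxon signed-rank test".

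The authors expect the first branch to apply most often: "Since we anticipate that most of our tests will involve continuous data that is normally distributed", which is why their power statement uses the paired t-test.

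The rule covers every continuous pre-post comparison. That includes the second primary objective in section B1, "The effect of LFD on hydrogen and methane levels in patients with bloating". The text does not say whether the check applies to baseline values, Day 21 values or their difference. It does not say what happens if the two visits give different answers. No other section adds to it.

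**The concern.** A paired t-test is a one-sample test on within-patient differences, so its normality assumption concerns the differences. Skewed values at each visit can still give normal differences, so a check on each visit can send an outcome to the wrong branch.

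The rule is also incomplete. With two visits there are two Shapiro-Wilk verdicts, and nothing is said about a split. The choice would then be made after the data are seen, with two p-values available, on outcomes that include a primary one. What would be at stake is the false-positive rate, the power, and the credibility of the reported result.

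**Working it through.** **The plan's own figure.** Inputs from B3.B: n = 20, two-sided alpha 5%, d = 0.5, pre-post correlation r = 0.7. The text claims that "a sample size of 20 will provide 80% power to detect a medium effect size".

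- Standardised effect on the differences: d / √(2(1 − r)) = 0.5 / √0.6 = 0.6455.
- Noncentrality: 0.6455 × √20 = 2.887.
- Power by noncentral t with 19 df: 78.2% (80% needs n = 21).
- Power by normal approximation: Φ(2.887 − 1.960) = 82.3% (80% needs n = 19).

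The stated 80% lies between the two. It reproduces, and the normality rule does not disturb it.

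**Does checking the wrong quantity matter?** Take an exponential patient effect with exactly normal differences, r = 0.7, n = 20 (4,000 simulated trials). Each visit is called non-normal in about 30% of trials, the differences in about 5%, and the visits disagree in about 27%. The cost is that some outcomes go to Wilcoxon needlessly. With normal differences and an assumed relative efficiency of 0.955, always using Wilcoxon gives about 76% power against 78.2% for the t-test. The loss is about 2 points even if every such outcome is misdirected.

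**Does a split verdict matter?** The rule was simulated with latent bivariate normal values, r = 0.7, n = 20, a shift of 0 or 0.5 SD, and 6,000 trials per setting (one standard error at most √(0.25/6000) = 0.65 points). Skewed settings exponentiate the latent values; those distributions are assumed. Both visits passing gives the t-test and both failing gives Wilcoxon. A split was resolved in three ways: t-test, Wilcoxon, or the smaller p-value. Ranges in the power column cover the three.

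| Data | Visits split | Split and tests disagree on significance (shifted) | Power, rule as written | Power, check on differences |
|---|---|---|---|---|
| Normal | 9.0–9.2% | 0.5% | 77.7–78.0% | 77.8% |
| Log-SD 0.3 | 30.4–31.1% | 2.1% | 73.8–75.0% | 74.2% |
| Log-SD 0.5 | 40.9–41.2% | 3.5% | 71.9–74.1% | 72.2% |
| Log-SD 0.75 | 27.9–28.1% | 3.2% | 68.9–71.3% | 69.3% |
| Log-SD 1.0 | 11.4–11.7% | 1.8% | 66.4–67.8% | 66.6% |

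- **Power.** The largest gap between the last two columns is 71.3 − 69.3 = 2.0 points.
- **Type I error.** It was 4.6–5.4% over all settings, even when the smaller p-value is taken on a split; a repeat of most settings gave 4.4–5.8%. This is expected. With no diet effect in these settings, the pre and post values are exchangeable, so the differences are symmetric about zero however skewed each visit is. Both tests then hold their level closely, and Shapiro-Wilk reacts to shape rather than to the shift being tested.
- **Consequential splits.** With no shift, a split with discordant tests occurred in 0.1–0.9% of trials. The highest rate in a repeat simulation was about 4%.

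**Over the whole trial.** The documents name about ten continuous outcomes: hydrogen, methane, bloating, IBS-SSS, three PROMIS scales, LPS, zonulin and tryptase. With normal data one expects 10 × 9% = 0.9 split verdicts, but only 10 × 0.5% = 0.05 that alter a significance call. At the worst setting in the table, with a true 0.5-SD effect on all ten, the figure is 10 × 3.5% = 0.35.

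**The case for a change.** The strongest case for a change is that the text is silent on both points, a primary outcome is affected, and a sentence would settle it. A split verdict is also not rare: about one outcome in ten even if the authors' expectation of normal data holds. Counting the change score as one of the continuous variables is a charitable reading, but the same check also decides between mean and median summaries, which points to visit-level values. All of that stands as a description of the text. It does not show a result that would come out materially different.

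A second argument is that skewed outcomes lose power because the rule never considers logs. Under the assumed log-normal model, a log-scale paired t-test had simulated power of 76.6–79.1%. The gap runs from 76.6 − 75.0 = 1.6 points at log-SD 0.3 to 77.1 − 66.4 = 10.7 points at log-SD 1.0. That gap comes from the scale of analysis, not from the normality check, and it needs a multiplicative effect on log-normal data. The documents give no distribution data. With gamma-distributed patient levels, an additive shift and normal within-patient noise, the direction reverses: 77–78% for the rule as written against 73–76% on the log scale.

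Naming one test per outcome in advance is a trade-off too. A fixed raw-scale t-test had 60–62% power at log-SD 0.75 and 49–51% at log-SD 1.0, where the rule as written had about 66–71%. Under strong skew the check protects power. Reserving Wilcoxon for markers with values below detection would bring back a choice made after seeing the data, because B3.A gives no detection limits for LPS, zonulin or tryptase.

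**Conclusion.** The observation is correct and no change to the plan follows. The silence about differences and split visits is missing detail of a kind an analyst fills in routinely, by checking the differences or by taking either test on a split. Every such choice leads to nearly the same place: Type I error near 5%, power within about 2 points, and a changed significance call in about 0.1–4% of runs per outcome (0.5% with normal data and the planned effect). The stated sample size and power are untouched.

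These figures assume 20 complete pairs, correlation 0.7 and the distributions listed above, of which only the normal case reflects what the plan expects. The larger gain claimed for a log scale depends on a model the documents do not give and reverses under another plausible one, so it cannot justify replacing the rule. Breath-test positivity is a proportion, so this rule does not bear on it.
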